mechanisms of insulin resistance, and the development of a non-invasive biomarker in children at an increased risk of developing insulin resistance.

Hypothesis and Specific Aims

We hypothesize that when compared to normal weight or obese insulin sensitive children, obese insulin resistant children will exhibit altered circulating blood cell bioenergetics and a more oxidized plasma redox state and that these alterations will be associated with decreased resting energy expenditure and impaired fatty acid oxidation (FAO). Furthermore, we hypothesize that poor oxidative capacity over time may distinguish between metabolically healthy obese (MHO) and metabolically unhealthy obese (MUO) phenotypes, as well as be predictive of T2D development. We also hypothesize that bioenergetics, REE and FAO will be improved in obese T2D or insulin resistant children after 6 months of metformin therapy that will be prescribed as part of their clinical care. To test these hypotheses, we will evaluate the following Specific Aims:

Specific Aim 1: Determine whether peripheral blood mononuclear cell (PBMC) and platelet bioenergetics (oxidative phosphorylation, glycolysis and fatty acid oxidation) are impaired and whether plasma glutathione-mediated redox/antioxidant capacity is decreased in obese insulin resistant children as compared to normal weight and obese insulin sensitive children.

Specific Aim 2: Determine whether resting energy expenditure (REE) and fatty acid oxidation (FAO) are decreased in obese insulin resistant as compared to lean and obese insulin sensitive children and whether REE and FAO are correlated with bioenergetic and redox profiles.

Specific Aim 3: Determine whether the bioenergetic oxidative capacity measured in circulating cells, PBMCs/platelets, and FAO are valuable predictive markers of T2D in obese children, in addition to distinguishing MUO from MHO subjects.

Specific Aim 4: Determine whether circulating blood cell bioenergetics and whole-body REE and FAO are modulated by metformin therapy that will be prescribed as part of clinical care in

Title: Bioenergetics and Metabolism in Pediatric Populations

PI: [name].

obese children with T2D or insulin resistance.

Study Design and Procedures

This study consists of:

1. An observational cross sectional bioenergetic and metabolic analysis of several groups of children including lean, obese, and T2D.

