At the time of collection, samples will be kept on ice or refrigerated (with the exception of stool which will be kept in a freezer) in the pediatric clinical research unit or in [name] laboratory (Rm 4015 of ACRI) until they can be transported to the research laboratory. Samples will be kept at -80°C once the initial processing and analyses have taken place. Samples will be stored in Room N2002 Freezer N2002FT6 or N2002FT18 of ACRI in [name] laboratory. These are monitored continuously for proper temperature and working condition. None of a subject's personal identifiers will be present on any biological sample, except the unique subject ID and the study acronym. The samples may be used until they are used up for research on pediatric nutrition.

At any time if the subject decides that he/she does not want to participate anymore, that subject's data will be included as part of the planned analysis of study data. No more information will be collected after withdrawal, however all data and samples collected prior to withdrawal will still be used.

Information pertaining to this study will be made publically available through the ClinicalTrials.gov website.

Data Analysis

Statistical and Power Analyses: 175 pre-pubertal children ages 5-9 years old will be recruited for this study assuming that 130 subjects stratified across the following groups will complete the study: i) healthy lean (n=20); ii) healthy obese (n=20); iii) obese insulin resistant (n=70); obese

Title: Bioenergetics and Metabolism in Pediatric Populations

PI: [name].

with new metformin prescription (n=20). A one-factor analysis of variance (ANOVA) will be used to compare mean outcome of interest across the groups of children (healthy lean, healthy obese, obese insulin resistant and obese T2D). Pair-wise comparisons using Tukey-Kramer post-hoc tests will be used to identify groups whose means differ significantly while retaining the family-wise error rate at 5%. Outcomes will be also checked to verify that the assumptions of the parametric tests are met. When substantial deviation from assumptions are encountered, and if suitable transformation are not found, groups will be compared using the nonparametric Kruskal-Wallis rank test, followed by Bonferroni corrected Wilcoxon rank-sum tests to identify groups that differ. Generalized linear model (GLM) will also be used to incorporate important covariates and effect modifiers into the analysis.

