For Aim 3: A paired t-test will be used to compare the mean change in the various outcomes described in SA1 and SA2 from baseline to 12 months for pre-pubertal insulin resistant obese children. If the assumptions for the paired t-test are not met, the non-parametric Wilcoxon matched-pairs signed-ranks test will be used. Alternatively, generalized linear mixed models (GLMM) will be used for Aim 3. GLMM account for the dependence between measurements from the same individual taken over time and allow the inclusion of fixed and time varying covariates.

For Aim 4: A paired t-test will be used to compare the effects of metformin on the various outcomes on obese T2D/insulin resistant children with a new metformin prescription. If the assumptions for the paired t-test are not met, the non-parametric Wilcoxon matched-pairs signed-ranks test will be used. Alternatively, generalized linear mixed models (GLMM) will be used for Aim 4. GLMM account for the dependence between measurements from the same individual taken over time and allow the inclusion of fixed and time varying covariates.

Sample Size Justification:

For Aims 1 and 2, statistical power was computed based on a one-factor ANOVA with a total of 110 children (70 obese insulin resistant, 20 healthy obese, 20 healthy lean). Assuming 80% power and $\alpha = 0.05$, the minimum detectable Cohen's f effect size (ES(f)) is 0.33. This is a medium effect size and should provide valuable information regarding whether a large study is warranted.

For Aim 3, statistical power was computed based on a paired t-test with a total of 40 children. Assuming 80% power and $\alpha = 0.05$, the minimum detectable Cohen's d effect size (ES(d)) is 0.45 for those who completed the study. These are medium effect sizes and should provide valuable information regarding whether a large study is warranted.

For Aim 4, statistical power was computed based on a paired t-test with a total of 10 children. Assuming 80% power and $\alpha = 0.05$, the minimum detectable Cohen's d effect size (ES(d)) is 1.0. Although this effect size is large, it should provide valuable information regarding whether a large study is warranted.

Ethical Considerations

This study will be conducted in accordance with all applicable government regulations and University of Arkansas for Medical Sciences research policies and procedures. This

Title: Bioenergetics and Metabolism in Pediatric Populations

PI: [name].

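### Aims 1 and 2 name two comparisons with the obese insulin-resistant group, but the plan corrects for all pairs of four groups, which costs power on those two and does not match the three-group power statement

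*Combined protocol and SAP*

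**What the plan says.** Under Hypothesis and Specific Aims, Aim 1 asks about bioenergetics and redox capacity "in obese insulin resistant children as compared to normal weight and obese insulin sensitive children". Aim 2 asks whether resting energy expenditure and fatty acid oxidation "are decreased in obese insulin resistant as compared to lean and obese insulin sensitive children"; it also has a correlation question, which is not at issue here.

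Under Data Analysis (Statistical and Power Analyses), a one-factor ANOVA compares means "across the groups of children (healthy lean, healthy obese, obese insulin resistant and obese T2D"). Then "Pair-wise comparisons using Tukey-Kramer post-hoc tests will be used to identify groups whose means differ significantly", with the family-wise error rate held at 5%. If assumptions fail and no transformation helps, a Kruskal-Wallis test is used, "followed by Bonferroni corrected Wilcoxon rank-sum tests to identify groups that differ". The number of tests in that correction is not stated. No contrast or pair is singled out as the one that answers an aim.

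Under Sample Size Justification, power for Aims 1 and 2 rests on a one-factor ANOVA "with a total of 110 children (70 obese insulin resistant, 20 healthy obese, 20 healthy lean"). The fourth group, 20 children with a new metformin prescription, is left out, and no power is given for any pairwise test.

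**The concern.** Four groups make six pairs. Two of them (insulin-resistant versus lean, insulin-resistant versus healthy obese) answer Aims 1 and 2. The other four (lean versus healthy obese, and three pairs with the metformin group) answer no question in those aims, yet they raise the critical value for the two that do. The comparator groups have only 20 children each, so power on the named comparisons is already limited.

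Three of the extra pairs are also hard to read. The inclusion criteria admit metformin participants up to 17 years 5 months with no Tanner limit, while the other groups are aged 5 to 9 and Tanner stage 1.

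The study is meant to show whether a larger one is warranted, so a true difference that is missed could end that line of work. The plan does not show the cost of the correction, because its power statement covers only the omnibus test and only three groups.

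**Working it through.** **The plan's own figure.** The Sample Size Justification gives a minimum detectable Cohen's f of 0.33 at 80% power and alpha 0.05. With noncentrality N·f², N = 110 and df 2 and 107, I get f = 0.300; power at f = 0.33 is 87.3%. The stated value does not reproduce but is on the cautious side. This is a separate matter and does not affect what follows. More relevant here, f describes the omnibus test and says nothing direct about either named comparison.

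**Inputs.** From the documents: group sizes 70, 20, 20 and 20; family-wise alpha 5%. Assumed: a common SD, two-sided tests, and a fourth ANOVA group consisting of the 20 metformin participants. The documents give no pairwise difference or SD, so I use a range of d (difference in SD units).

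**Standard error** of one named contrast, in SD units: √(1/70 + 1/20) = 0.2535.

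**Critical t values.**
- Tukey, four groups, error df 130 − 4 = 126: q/√2 = 2.604 (about 0.0103 per pair).
- Tukey, three groups, error df 110 − 3 = 107: q/√2 = 2.377.
- Dunnett, two contrasts with the insulin-resistant group as reference, correlation 20/(20 + 70) = 0.222: 2.258 with 126 df (about 0.0257 per contrast) or 2.263 with 107 df.
- Bonferroni for two tests, 126 df: 2.269.

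**Power for one named contrast**, from the noncentral t with noncentrality d/0.2535:

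| d | Tukey, 4 groups (126 df) | Dunnett, 2 contrasts (126 df) | Loss (points) | Tukey, 3 groups (107 df) | Dunnett, 2 contrasts (107 df) | Loss (points) |
|---|---|---|---|---|---|---|
| 0.5 | 26.8% | 39.0% | 12.2 | 34.7% | 38.9% | 4.2 |
| 0.6 | 40.9% | 54.4% | 13.5 | 49.8% | 54.3% | 4.5 |
| 0.7 | 56.4% | 69.2% | 12.9 | 65.0% | 69.1% | 4.1 |
| 0.8 | 70.9% | 81.4% | 10.5 | 78.1% | 81.2% | 3.2 |
| 1.0 | 90.8% | 95.3% | 4.5 | 94.0% | 95.2% | 1.2 |

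(Losses are from unrounded powers, so the last digit may differ from the rounded columns.)

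**Detectable d at 80% power.** Four-group Tukey 0.875; three-group Tukey 0.817; two Dunnett contrasts 0.787 (126 df) or 0.788 (107 df).

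**Equivalent in children.** Under four-group Tukey at d = 0.788, power is 79.5% with 26 per comparator group and 80.8% with 27. Matching the two-contrast plan would therefore take about 27 per comparator group instead of 20.

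**Link to the plan's f.** If f = 0.33 arises because the insulin-resistant group differs equally from both comparators, then d = 0.33/√[(70/110)(40/110)] = 0.69. Power per contrast is then 54.2% under four-group Tukey and 67.3% under Dunnett. That pattern of means is an illustration, not something the plan states.

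**Rank fallback.** If Bonferroni covers six pairs, each is tested at 0.05/6 = 0.0083 instead of 0.05/2 = 0.025. On the t scale, power at d = 0.8 is 68.2% against 81.1%.

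**The case against.** Tukey-Kramer suits unequal groups and is conservative for the two named contrasts. A reader might infer that the plan produces false positives; it does not. That stands: the issue is efficiency and fit.

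A reader might also infer that the four other pairs have no place in the study. The documents do not support this. Study Design and Procedures describes the cross-sectional part as covering lean, obese and T2D children, so pairs with the metformin group belong to the design. Lean versus healthy obese helps separate adiposity from insulin resistance. These are reasons to estimate those pairs, but not to let them set the critical value for Aims 1 and 2.

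The strongest objection is that the Sample Size Justification points to a three-group analysis. If that is what is meant, most of the loss disappears. This stands as a condition on the size. It does not remove the point, because the analysis text lists four groups and the two sections need to agree.

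The six-test Bonferroni count is an inference. Six is the natural reading after a four-group Kruskal-Wallis test, but the text would also allow two.

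The planned generalized linear model with covariates may change precision. It does not say which comparisons decide the aims or how they are corrected.

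**Conclusion.** The point holds as a loss of efficiency and a mismatch between the aims, the analysis and the power statement. It is worth correcting because correction is cheap; it is not an error that invalidates the analysis.

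It is tempting to sum up the cost as a flat 10 points of power. The documents do not support that, since they give no pairwise effect size and disagree on the number of groups. For d from 0.5 to 1.0, the loss runs from 13.5 points down to 4.5 under the four-group text, and from 4.5 down to about 1 under a three-group reading. These figures assume a common SD, two-sided tests and full groups of 70 and 20. The arithmetic is firm; which range applies depends on the sponsor's intention.

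**What to change.** - For Aims 1 and 2, pre-specify two contrasts: insulin-resistant versus lean, and insulin-resistant versus healthy obese. Control them jointly at 5% with Dunnett (insulin-resistant group as reference) or Holm, and do not make them conditional on the omnibus F.
- In the rank fallback, state that the correction covers these two tests.
- Keep lean versus healthy obese and the metformin/T2D pairs as secondary estimates with confidence intervals, outside this family.
- Reconcile the four groups in the analysis text with the three in the Sample Size Justification, say which groups supply the error variance, and give power for the two contrasts.

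The cost is wording in the analysis plan, with no added children, visits or samples. The small downside is that the secondary pairs, which the cross-sectional design includes or which help interpretation, lose a test under family-wise control.

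### With one group of 70 and the others of 20, the stated 5% family-wise error rate for Aims 1 and 2 depends on equal group variances, and the planned fallback only partly repairs a departure

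*Combined protocol and SAP*

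**What the plan says.** Under Data Analysis (Statistical and Power Analyses), the plan states: "A one-factor analysis of variance (ANOVA) will be used to compare mean outcome of interest across the groups of children". The groups listed are "healthy lean, healthy obese, obese insulin resistant and obese T2D". It continues: "Pair-wise comparisons using Tukey-Kramer post-hoc tests will be used to identify groups whose means differ significantly while retaining the family-wise error rate at 5" percent.

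Three steps follow.

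- **Check.** "Outcomes will be also checked to verify that the assumptions of the parametric tests are met". No test or threshold is named.
- **Transform.** If the departure is substantial, a suitable transformation is sought first.
- **Ranks.** If none is found, "groups will be compared using the nonparametric Kruskal-Wallis rank test", followed by Bonferroni-corrected Wilcoxon rank-sum tests.

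A GLM is added for covariates, with no provision for unequal variances. No Welch, Games-Howell or robust-variance method is named.

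Under Sample Size Justification, the Aim 1 and 2 calculation uses "70 obese insulin resistant, 20 healthy obese, 20 healthy lean". The Data Analysis section adds a fourth group of 20, the children with a new metformin prescription. No group standard deviations appear anywhere in the documents.

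**The concern.** Tukey-Kramer and the classical F test estimate one common variance. With three groups, the 70-child group carries 69 of the 107 error degrees of freedom, so the pooled value is largely that group's variance. If the 20-child groups are more variable, standard errors for comparisons involving them are too small and false differences appear. If the 70-child group is more variable, standard errors are too large and real differences are missed.

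The rank fallback is the plan's last remedy for failed assumptions. Kruskal-Wallis and Wilcoxon tests hold their level when the distributions are identical under the null. Equal centers with unequal spread do not meet that condition, and unequal group sizes make it worse.

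The comparisons at stake are the hypotheses of Aims 1 and 2: insulin-resistant obese children against lean and insulin-sensitive obese children. The results are also meant to show whether a larger study is justified. That decision can be misled in either direction.

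**Working it through.** **Inputs from the documents.** Group sizes 70/20/20 (Sample Size Justification) and 70/20/20/20 (Data Analysis); α = 0.05; Tukey-Kramer; fallback of Kruskal-Wallis, then Wilcoxon at 0.05/3 (three groups) or 0.05/6 (four).

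**Assumptions.** The ratio of group SDs is not given, so it was varied in both directions. The fallback trigger is not defined and was taken as a Brown-Forsythe test at 5%. Means are equal and data normal. Each scenario has 20,000 datasets; the simulation standard error at 5% is √(0.05 × 0.95 / 20,000) ≈ 0.15 percentage points.

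**Step 1: the plan's own figure.** With equal variances, Tukey-Kramer gives 5.0–5.1% at 70/20/20 and 4.7–5.0% at 70/20/20/20. The stated 5% reproduces under that condition.

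**Step 2: why it moves.** Tukey-Kramer declares a difference when |mᵢ − mⱼ| / √[(MSE/2)(1/nᵢ + 1/nⱼ)] exceeds the studentized-range quantile, with MSE = Σ(nᵢ − 1)sᵢ² / (N − k).

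*SDs 1, 2, 2 (small groups more variable).* Expected MSE = (69×1 + 19×4 + 19×4)/107 = 221/107 = 2.065.
- 20 v 20: assumed variance 2.065 × 0.1 = 0.207; true variance 4/20 + 4/20 = 0.400. The standard error is √(0.207/0.400) = 0.72 of what it should be.
- 70 v 20: assumed 2.065 × (1/70 + 1/20) = 0.133; true 1/70 + 4/20 = 0.214. Ratio of standard errors 0.79.

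*SDs 2, 1, 1 (large group more variable).* Expected MSE = (69×4 + 19 + 19)/107 = 314/107 = 2.935.
- 20 v 20: 0.293 against 0.100. Ratio 1.71.
- 70 v 20: 2.935 × 0.0643 = 0.189 against 4/70 + 1/20 = 0.107. Ratio 1.33.

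**Step 3: family-wise error at 70/20/20.** The whole plan uses Tukey-Kramer unless the variance check fires, and otherwise Kruskal-Wallis then Wilcoxon.

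| SD, 70-group : 20-groups | Check fires | Tukey-Kramer alone | Kruskal-Wallis then Wilcoxon | Whole plan |
|---|---|---|---|---|
| 1 : 1 | 4.2% | 5.1% | 4.0% | 5.1% |
| 1 : 1.25 | 20.5% | 8.4% | 5.0% | 7.5% |
| 1 : 1.5 | 60.0% | 11.1% | 6.2% | 7.9% |
| 1 : 2 | 97.2% | 16.1% | 8.3% | 8.5% |
| 1 : 3 | 100% | 21.5% | 11.1% | 11.1% |
| 1.25 : 1 | 20.3% | 2.6% | 2.7% | 2.8% |
| 1.5 : 1 | 59.3% | 1.3% | 1.8% | 1.7% |
| 2 : 1 | 97.8% | 0.4% | 1.0% | 1.0% |

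At modest ratios the check usually does not fire, so Tukey-Kramer is kept. At larger ratios the fallback is used but is itself off 5%. Separate runs of the whole plan gave up to about 9% at ratios 1.25–2, so 7.5–9% is a fair summary.

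**Step 4: the four listed groups (70/20/20/20).** With the small groups 1.25, 1.5 and 2 times as variable, the whole plan gives 7.6%, 7.5% and 7.2%, and Tukey-Kramer alone 8.5%, 11.2% and 15.6%. With the large group 1.5 and 2 times as variable, the whole plan gives 1.6% and 0.8%. The conclusion is unchanged.

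**Step 5: group sizes.** At 37/37/36 with SD ratio 2, Tukey-Kramer is at 5.5–5.9%. The planned imbalance drives the problem.

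**Step 6: the alternative.** Over three and four groups and SD ratios up to 3 in either direction, Games-Howell gave 4.5–5.3% and Welch's ANOVA 4.6–5.3%. Smaller runs put Games-Howell at up to 6%.

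**Step 7: power.** Both 20-child groups are placed 0.8 units from the 70-child group; the small-group SD is 1.

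| Large-group SD | One 70 v 20 pair: Tukey-Kramer | Same pair: Games-Howell | Any pair: whole plan | Any pair: Games-Howell |
|---|---|---|---|---|
| 1 | 78% | 75% | – | – |
| 1.5 | 48% | 63–65% | 64% | 82% |
| 2 | 24–25% | 52% | 40% | 68% |

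**The case against.** The plan does not apply Tukey-Kramer blindly: it checks assumptions, tries a transformation, and only then moves to ranks. Four points follow.

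- **The transformation step is real.** Where spread rises with the mean, a transformation may remove the problem. It cannot equalize spread between groups that share a mean, which is the case simulated here. This limits the concern without removing it.
- **The fallback does help.** When used, it gives 5.0% and 6.2% at ratios 1.25 and 1.5, close to nominal. A reader might infer from the Tukey-Kramer column that the plan runs at 11–17% error. The documents do not support that, because the plan says a substantial departure will not be left to Tukey-Kramer.
- **Size and direction are unknown.** A reader might also infer that the comparisons are badly anti-conservative. Without any SDs, inflation is no better supported than conservatism. One pattern gives little trouble: with both obese groups at 1.5 times the lean SD, Tukey-Kramer error is 3.3%. The eligibility criteria give some reason to expect unequal spread: the metformin group admits ages 5 to 17 years 5 months without the Tanner limit set for the 5–9-year-olds. If that group alone has 1.5 times the SD, Tukey-Kramer is at about 8% and the whole plan at about 6–7%. At 2 times, however, the whole plan is at 4.4%.
- **The 5% statement is correct under its own assumption,** and the study is observational and exploratory, with no outcome named as primary. That lowers the stakes.

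What stands is that the plan's sequence does not hold 5% over a plausible range of SD ratios, while a standard method does.

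**Conclusion.** The point holds in a limited form. At the planned group sizes, the stated 5% family-wise rate is conditional on roughly equal variances, and the check–transform–rank sequence restores it only in part. For SD ratios of 1.25 to 2, whole-plan error is about 7.5–9% if the 20-child groups are the more variable. If the 70-child group is 1.5 to 2 times as variable, it is about 1–2%, with a material loss of power. These figures rest on assumed SD ratios, normal data with equal means (except the power runs), no effective transformation, and a Brown-Forsythe 5% trigger in place of the plan's undefined one. The documents show neither that variances will differ nor in which direction. This is an inexpensive improvement to the method rather than a flaw that invalidates the comparisons.

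**What to change.** For Aims 1 and 2, name Welch's ANOVA with Games-Howell pairwise tests as the default for all outcomes, without a preliminary variance test. Specify heteroscedasticity-consistent standard errors for the covariate-adjusted GLM. Keep transformation and the rank tests for gross non-normality only, and do not present them as the remedy for unequal variances.

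This changes a sentence or two in the Data Analysis section and needs no further children, visits or samples. It also ends reliance on an undefined, data-driven switch for unequal spread. If variances are in fact equal, the cost is about 1–3 percentage points of power per pair (for example, 75% against 78%).

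### The rank-test fallback is valid but needlessly conservative: a step-down correction in place of single-step Bonferroni would gain power within the same 5% family-wise ceiling

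*Combined protocol and SAP*

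**What the plan says.** The paragraph Statistical and Power Analyses, under Data Analysis, plans a one-factor ANOVA across four groups ("healthy lean, healthy obese, obese insulin resistant and obese T2D"). Tukey-Kramer comparisons follow, "while retaining the family-wise error rate at 5" per cent.

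The fallback has a condition: "When substantial deviation from assumptions are encountered, and if suitable transformation are not found". In that case the plan turns to the "nonparametric Kruskal-Wallis rank test, followed by Bonferroni corrected Wilcoxon rank-sum tests to identify groups that differ".

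Three things are left open:
- whether the pairwise tests are run only after a significant Kruskal-Wallis test;
- how many pairs Bonferroni divides by;
- whether the 5% stated for Tukey-Kramer is also the target on the rank route.

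The same paragraph gives planned group sizes of 20 healthy lean, 20 healthy obese, 70 obese insulin resistant and 20 with a new metformin prescription. The Sample Size Justification for Aims 1 and 2 uses only the first three groups, 110 children in all. It sizes the overall ANOVA and claims no power for any pairwise test or for the rank route.

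**The concern.** Aim 1 rests on two comparisons: insulin-resistant children against normal-weight children, and against obese insulin-sensitive children. Each comparator has only 20 children, so pairwise power is scarce.

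Single-step Bonferroni judges every pair as if all pair hypotheses could still be true. Once one pair has been rejected, or Kruskal-Wallis has rejected equality of all groups, that is no longer possible. A correction that keeps the same divisor throughout leaves part of the 5% unused. What is at stake is missed differences on the rank route, not false positives.

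**Working it through.** **Inputs.** Group sizes 70/20/20 and 70/20/20/20 and the 5% level come from the documents. The documents give no pairwise effect, so a shift of 0.7 SD in the insulin-resistant group is assumed. All pairs are taken as tested: 3 with three groups, 6 with four.

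**The plan's own figure.** There is none for this route. The nearest, Cohen's f = 0.33 in the Sample Size Justification, concerns the overall ANOVA and is not an input here.

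**Step 1. Why single-step Bonferroni falls below 5%.** The family-wise error is at most (true null pairs) × 5% / (all pairs).

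| Groups | Pattern | True null pairs | Bound | Simulated, Kruskal-Wallis then Bonferroni |
|---|---|---|---|---|
| 3 | all equal | 3 | 3 × 5%/3 = 5% | 3.7% |
| 3 | one differs | 1 | 1 × 5%/3 = 1.67% | 1.4-1.6% |
| 4 | all equal | 6 | 6 × 5%/6 = 5% | 3.0% |
| 4 | one differs | 3 | 3 × 5%/6 = 2.5% | about 2.0% |
| 4 | two against two | 2 | 2 × 5%/6 = 1.67% | 1.4-1.5% |
| 4 | one pair equal | 1 | 1 × 5%/6 = 0.83% | 0.7% |

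The simulations use the chi-square Kruskal-Wallis test and two-sided Wilcoxon tests by normal approximation. The all-equal rows lie below the bound mainly because the pair tests are correlated. The other rows are low because few true nulls remain while the divisor stays at 3 or 6.

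**Step 2. What the Kruskal-Wallis step adds.** Without it, Bonferroni alone gives 4.0% (three groups) and 3.4% (four) when all groups are equal, and essentially the same values as above in the other rows. At 0.7 SD with three groups, power for the two insulin-resistant comparisons is 57.2% and 58.6% with the step and 57.3% and 58.6% without. Across the patterns examined it costs at most 0.8 points per pair.

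**Step 3. Step-down thresholds.** With three groups, the possible numbers of true pair hypotheses are 3, 1 or 0. With four they are 6, 3, 2, 1 or 0. Once equality of all groups is rejected, at most 1 (three groups) or 3 (four groups) can remain.
- Holm, with no precondition: divisors 3, 2, 1 for three groups; 6, 5, 4, 3, 2, 1 for four.
- Shaffer, after a significant Kruskal-Wallis test at 5%: each pair at 5% for three groups; divisors 3, 3, 3, 3, 2, 1 for four, so thresholds of 1.67% four times, then 2.5%, then 5%.

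**Step 4. Power at 0.7 SD.** Ranges reflect the different comparisons and separate simulation runs.

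| Groups | Procedure | Each insulin-resistant comparison | Both comparisons |
|---|---|---|---|
| 3 | Kruskal-Wallis, Bonferroni | 57-59% | 38.5% |
| 3 | Holm | 61-63% | 5-7 points more |
| 3 | Kruskal-Wallis, Shaffer | 73% | 59% |
| 4 | Kruskal-Wallis, Bonferroni | 48-50% | 27% |
| 4 | Holm | 51-53% | 5-7 points more |
| 4 | Kruskal-Wallis, Shaffer | 58-59% | 38-39% |

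**Step 5. Error under the Shaffer thresholds.** All groups equal: 5.0% (three groups) and 4.2% (four). One group shifted by 1.5 SD: 4.7% and 4.0%. None exceeds 5%.

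**The case against.** The strongest reply is that the planned fallback is a standard, valid procedure, so choosing a sharper one is a matter of efficiency on a contingent route. Most of this stands. The 5% is a ceiling, it is attached to Tukey-Kramer, and the fallback respects it. Tukey-Kramer itself falls to 2.0-2.9% in the four-group layout when two or three null pairs remain, so being under 5% is not peculiar to the rank route. The documents claim no pairwise power that is then missed.

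The route may also be rare. A lognormal outcome would be repaired by a log transform and stay with ANOVA. Rank tests are unchanged by such a transform, so the figures above describe a simple shift. For outcomes that no transformation repairs, the gain could differ.

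A reader might infer more than the documents support:
- That the plan corrects twice, and that the Kruskal-Wallis step causes the loss. Step 2 rules this out, and dropping that step would restore almost nothing.
- That Kruskal-Wallis is a stated precondition and that Bonferroni covers every pair. The text says neither; both are readings of it.
- That the error rate is 1-3% throughout, or that 10-15 points of power are lost in any case. With three equal groups the error is nearer 4%, and with plain Holm the gain is only 3-4 points per comparison.

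What the reply does not remove is that a step-down correction is equally strict and at least as powerful, for one sentence of text.

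**Conclusion.** The point holds as a minor efficiency improvement. The fallback breaks no stated error rate and no power claim.

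The power gains rest on the assumed 0.7 SD shift, the planned group sizes being reached, and all pairs being tested; they shrink for large effects. Two statements do not depend on the effect size. Holm never rejects fewer pairs than Bonferroni. Shaffer after Kruskal-Wallis never rejects fewer than Bonferroni after Kruskal-Wallis. If the plan intends no precondition, adding one for the Shaffer thresholds could occasionally lose a pair that Bonferroni alone would have found, at the small cost shown in Step 2.

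**What to change.** Before analysis, replace the words specifying Bonferroni on the rank route with one of these:

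1. **No precondition:** Holm-adjusted pairwise Wilcoxon tests at a family-wise 5%.
2. **Precondition declared:** pairwise tests only if Kruskal-Wallis is significant at 5%. With three groups, test each pair at 5%. With four, compare the ordered p-values with 5% divided by 3, 3, 3, 3, 2, 1, stopping at the first that fails.

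State in the same sentence how many groups and pairs enter, since the analysis paragraph lists four groups and the sample size paragraph three. This matters for option 2: testing each pair at an unadjusted 5% after Kruskal-Wallis is valid with three groups, but with four it gives a family-wise error of about 9-12% when some groups are equal and others differ.

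The cost is one sentence, with no further children or data. Step-down tests have no matching simultaneous confidence intervals.
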